### Imputation of Missing Efficacy Data

The primary method of handling of missing efficacy data will utilize Multiple Imputations (MI). Last observation carried forward (LOCF) method will be used as supportive analysis of the primary and secondary endpoints. For sensitivity analysis of the primary and secondary endpoints, missing data will be imputed as Treatment Failures (TF). Only missing data up to Week 12 will be imputed. Missing data at the Week 16 Follow-up visit will be analyzed as Observed Cases (OC) only.

MI: For the MI model, 100 imputations will be generated using PROC MI of SAS. Fully Conditional Specification (FCS) model using the regression method will be used with the response (e.g., PGA score) at prior post-baseline visits, baseline PGA score, baseline value of the corresponding endpoint, and treatment group as covariates, The ROUND and MINIMUM options will be utilized to ensure imputed values are non-negative integers. The seed to be used in all MI model is 20180330.

One set of MI datasets will be generated for the PGA scores, PASI scores and %BSA results separately. Response status (Yes, No) will be derived from the imputed scores in each MI dataset. Analysis of each primary, secondary and exploratory outcome will then be performed for each of the relevant MI datasets. The results of the 100 analyses will be transformed into a normal statistic and combined into a single analysis using PROC MIANALYZE.

Example SAS code for the PGA scores is as follows:

```
PROC MI DATA = PGA1 OUT = PGA2 SEED = 20180330 NIMPUTE = 100 NOPRINT;
CLASS TRTPN BASEPGA;
FCS LOGISTIC(BASEPGA = TRTPN / DETAILS);
FCS REG(PGA3 = TRTPN BASEPGA / DETAILS);
FCS REG(PGA4 = TRTPN BASEPGA PGA3 / DETAILS);
FCS REG(PGA5 = TRTPN BASEPGA PGA3 PGA4 / DETAILS);
FCS REG(PGA6 = TRTPN BASEPGA PGA3 PGA4 PGA5 / DETAILS);
VAR TRTPN BASEPGA PGA3-PGA6;
RUN:
```

The imputation models may be modified based on the actual data if there is an issue in model convergence.

**LOCF:** The last observed value will be carried forward for any subsequent missing values. Baseline values will not be carried forward.

**TF**: missing data will be imputed as treatment failures for responder endpoint.

Missing functional outcomes, quality of life endpoints or safety endpoints will not be imputed.

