#### Calculation of %BSA Affected:

Measurement of involved BSA is estimated by the handprint method: the total palmar surface of the subject's palm and digits is approximately 1% of their total BSA.

Estimate the involved regional area by determining the number of "full" handprints plus the number of handprints covered if several smaller lesions are "pushed together." Each region can have up to 100% involvement.

- Head and neck = 10% of overall BSA (10 handprints);
   1 hand-sized plaque ~ 10% of head and neck area
- Upper extremities = 20% of overall BSA (20 handprints);
   1 hand-sized plaque ~ 5% of the upper extremities
- Trunk (including axillae and groin) = 30% of overall BSA (30 handprints); 1 hand-sized plaque ~ 3.33% of the trunk
- Lower extremities (including buttocks) = 40% of overall BSA (40 handprints);
   1 hand-sized plaque ~ 2.5% of the lower extremities

Estimates of the % involvement in each body region will be multiplied by the fraction of total body area to obtain the total %BSA involved by region and overall.

Body Region	% Involvement for Each Region (0-100%)	Multiplier	Regional %BSA Involvement
Head and neck		x 0.1	=
Arms/upper extremities		x 0.2	=
Trunk		x 0.3	=
Legs/lower extremities		x 0.4	=
TOTAL Involve	d %BSA – sum of the 4 regiona	d values (0-100%)	=

Note: Shaded cells are either fixed values or will be calculated in the eCRF and/or the IVRS/IWRS. Multiplier is a fixed number representing fraction of total body area.

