#### **Calculation of PASI:**

Use the % Iinvolvement for Each Region (0-100%) column from the table above to convert each percentage to individual area scores (0 to 6; PASI Item 5) based on the following categories:

Percentage of skin covered with psoriasis for each of the 4 areas									
Affected	0%	< 10%	10 - < 30%	30 - < 50%	50 - < 70%	70 - < 90%	≥ 90%		
Score	0	1	2	3	4	5	6		

Using the table below, for Items 1, 2, and 3, generate an average score for erythema, thickness, and scale for each of the 4 body areas using the following 5-point scale: 0=None; 1=Slight; 2=Mild; 3=Moderate; 4=Severe.

				Bod	ly Area	
Ite m	Assessment		Head/ Neck	Upper extremities (arms)	Trunk (to groin)	Lower extremities (leg to top of buttocks)
1	Erythema (redness)	(0-4)				
2	Induration (thickness)	(0-4)				
3	Scale (desquamation)	(0-4)				
4	Sum of Items 1, 2, and 3	(0-12)				
5	Area Score	(0-6)				
	Area Multiplier		0.1	0.2	0.3	0.4
6	Score of (Item 4) x (Item 5) x (Area Multiplier)		Item 4 x Item 5 x 0.1	Item 4 x Item 5 x 0.2	Item 4 x Item 5 x 0.3	Item 4 x Item 5 x 0.4
7	Sum of Item 6 for each column is the total PASI score	(0-72)				

Note: Items in shaded rows will be calculated in the eCRF.

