### 7. SAMPLE SIZE DETERMINATION

It is assumed that the proportion of subjects who achieve PGA score of clear (0) or almost clear (1) with a minimum 2-grade improvement from Baseline at Week 12 will be 40% for subjects receiving tapinarof compared with 15% for subjects receiving vehicle control. With 500 subjects randomized in a 2:1 ratio (approximately 333 subjects receiving tapinarof cream, 1% and approximately 167 subjects receiving vehicle cream) there will be > 99% power for statistical significance (2-sided p< 0.05). If tapinarof response rate is 35%, and vehicle response rate is 20%, the power will be > 94%. Power comes from a Fisher Exact sample size calculation which is conservative. It is assumed that up to 25% of the subjects will be lost to follow-up by 12 weeks. These subjects will be included in the primary analysis in the ITT population using the multiple imputation method as detailed below.

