### 11.4 Analysis Visit Window

All efficacy and safety endpoints will be analyzed according to the nominal visits (i.e. actual visit) except for assessments collected on early termination and unscheduled visits. Early termination and unscheduled visits will be re-numbered to an analysis visit based on their windowed visits defined by actual study day. If more than one visit occurs within a single visit window, then the analysis will take the one closest to the target day. If the 2 visits are equidistant from the target day, the visit with later date and time will be used.

The following analysis visit windows will apply to early termination and unscheduled visits:

Visit	Week	Target Day	Analysis Window
2	Baseline	1	On or prior to Day 1
3	2	15	Post first dose – Day 21
4	4	29	Day 22 – Day 42
5	8	57	Day 43 – Day 70
6	12	85	Day 71 – Maximum (last day of treatment + 3 days,
			Day 87)
7	16	113	> Maximum (last day of treatment + 3 days, Day 87)

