### 13. CHANGES FROM THE PROTOCOL AND PLANNED ANALYSES

The protocol specified change over time in physical component score and mental component score as measured by the SF-36 questionnaire as an exploratory endpoint. Scoring rules for the RAND 36-Item Health Survey (Version 1.0) are provided for the eight domain scores but not for the physical component score or the mental component score. Hence, summaries of the eight domain scores are planned.

No other changes from the protocol in planned analyses are noted. Any additional statistical analyses to handle modifications to study conduct and/or missing data due to the COVID-19 pandemic have been documented in Section 12.11 above in this SAP and will be finalized prior to database lock and unblinding of the study.

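### SAP 9 forces imputed PASI and %BSA to non-negative integers from a normal regression: response cut-offs for imputed subjects shift with baseline, and the PASI-75 difference shrinks modestly

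*SAP*

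**What the plan says.** SAP 9 (Imputation of Missing Efficacy Data) has one MI specification: 100 imputations by FCS linear regression on treatment, baseline PGA, the endpoint's own baseline value and earlier post-baseline visits. It adds: "The ROUND and MINIMUM options will be utilized to ensure imputed values are non-negative integers". Protocol 10.6 carries the same constraint. SAP 9 then sets the scope: "One set of MI datasets will be generated for the PGA scores, PASI scores and %BSA results separately". Responder status is derived from the imputed scores. PGA is named only as an example of the response variable, and no other rule is given for PASI or %BSA. One departure is foreseen: "The imputation models may be modified based on the actual data if there is an issue in model convergence". The sample code covers PGA only and shows neither option.

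Protocol Appendix 3 builds PASI from regional sign scores times an area score times a multiplier of 0.1 to 0.4. For %BSA it says: "Estimates of the % involvement in each body region will be multiplied by the fraction of total body area".

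The table in SAP 12.8 makes MI in the ITT population the primary analysis of the secondary endpoints. In SAP 11.6, PASI-75 is tested first, change in %BSA third and PASI-90 fourth.

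**The concern.** A non-negative integer constraint suits a 0-4 global score. It does not suit PASI or %BSA, which are skewed, bounded at 0 and not restricted to integers. Two consequences follow for subjects with an imputed Week 12 value:

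- The improvement that counts as PASI-75 or PASI-90 is no longer 75% or 90%. It depends on where baseline falls relative to the integer grid.
- A normal draw with one residual variance for both arms misplaces probability near 0, which is where the responder cut-offs lie.

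At stake is the primary estimate for three of the four secondary endpoints, including PASI-75, which must succeed before the later ones are tested.

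**Working it through.** **The plan's own figure.** The documents give no figure for PASI imputation. The nearest is the primary-endpoint power in SAP 7 (333 v 167, two-sided 0.05): above 99% for 40% v 15% and above 94% for 35% v 20%. Exact Fisher enumeration gives more than 99.9% and 93.8%. The pooled normal formula for 35% v 20% runs:

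- Pooled rate: (333×0.35 + 167×0.20)/500 = 0.300
- Null SE: √[0.300×0.700×(1/333 + 1/167)] = 0.0434
- Alternative SE: √(0.35×0.65/333 + 0.20×0.80/167) = 0.0405
- Power: Φ[(0.15 − 1.96×0.0434)/0.0405] = Φ(1.60) = 94.5%

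The stated power is reproduced to within rounding.

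**Scales.** With whole-number sign scores, the Appendix 3 multipliers put PASI on a 0.1 grid. For %BSA, 5% of head and neck contributes 5 × 0.1 = 0.5% BSA, so fractions are possible.

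**Cut-offs (arithmetic only).** Let b be baseline PASI and q = 0.25 (PASI-75) or 0.10 (PASI-90). An imputed integer counts as response if it is at most k = floor(q·b), so the draw must fall below k + 0.5. Improvement needed = 1 − (k + 0.5)/b.

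| Endpoint | b | k | Needed |
|---|---|---|---|
| PASI-75 | 3.0 | 0 | 83.3% |
| PASI-75 | 3.9 | 0 | 87.2% |
| PASI-75 | 4.0 | 1 | 62.5% |
| PASI-75 | 6.0 | 1 | 75.0% |
| PASI-75 | 7.9 | 1 | 81.0% |
| PASI-75 | 8.0 | 2 | 68.8% |
| PASI-75 | 10.0 | 2 | 75.0% |
| PASI-90 | 3.0 | 0 | 83.3% |
| PASI-90 | 5.0 | 0 | 90.0% |
| PASI-90 | 9.9 | 0 | 94.9% |
| PASI-90 | 10.0 | 1 | 85.0% |

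For PASI-75 the requirement is too lenient from 4k to 4k+2 and too strict from 4k+2 to 4k+4, which is why the shifts largely cancel over a spread of baselines. If all three signs score 3 (an assumption), BSA of 3-20% gives a weighted area sum of 0.3 to 2.5. Times 9, that is PASI 2.7 to 22.5, a range that spans these breakpoints.

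**Effect on the PASI-75 difference (simulated).** The documents give no baseline PASI, PASI response rates or PASI missingness, and do not say how MINIMUM treats a negative draw. All of these are assumed, and both behaviours of MINIMUM are shown. Dropout was random; the 27-scenario set and the wider grid made it monotone and imputed visit by visit, regressing on treatment, baseline PGA, baseline PASI and prior visits. The 27-scenario set used baseline mean/SD of 7/3, 9/4 and 12/5 and PASI-75 rates of 38.5 v 9%, 25 v 10% and 30 v 15%. The wider grid used the PGA planning rates plus 40 v 8%, with spread differing by arm. Change in the whole-trial difference at 25% missing, in points:

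| Assumed set | Redrawn | Set to 0 |
|---|---|---|
| 27 scenarios | −0.9 to −4.1 | −0.3 to −1.8 |
| 18 scenarios | −0.9 to −3.6 | 0 to −2.0 |
| 8 scenarios | −1.8 to −4.5 | −0.6 to −2.0 |
| Same spread in both arms | −1.1 to −3.6 | 0 to −1.9 |
| Bimodal response | −1.5 to −4.5 | −1.5 to −3.6 |
| Wider grid (288) | −1.0 to −5.8 | −0.7 to −3.6 |

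**Where the shrinkage comes from.** Rounding alone moved the difference by 0.1 or less in the 27 scenarios (median 0.0 in the wider grid). Normal regression with neither floor nor rounding already gave −0.1 to −1.6 in the 18 scenarios. In the wider grid the floor added a median of about −1.3 points if negatives are redrawn and about −0.1 if they are set to 0. The small second figure is expected, because a negative Week 12 draw already counts as a response.

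**Less missing data (27 scenarios; 5 / 10 / 15% missing).** Redrawn: −0.2 to −0.8 / −0.3 to −1.6 / −0.5 to −2.4. Set to 0: 0.0 to −0.3 / −0.1 to −0.7 / −0.1 to −1.1.

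**Other endpoints at 25% missing.** The PASI-90 difference changed by −0.5 to −3.4 (redrawn) or −0.6 to +1.0 (set to 0). The %BSA mean difference was 2.7-6.0% smaller (redrawn) or 1.3-3.2% smaller (set to 0), all from the floor.

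**Power for PASI-75.** Running the stratified relative-risk analysis with Rubin's rules (1,500 trials of 333/167, 25% missing) gave, for matching / set to 0 / redrawn, 97.2 / 96.9 / 96.1% at 25 v 10% and 92.6 / 92.5 / 91.0% at 30 v 15%. The Monte Carlo standard error is about √(0.92×0.08/1500) = 0.7 points.

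**The case against.** The strongest reply is that the quoted constraint does little harm on average. Rounding has almost no net effect, and extreme baselines make the cut-off table look worse than the aggregate. If negatives are set to 0, what remains is mostly an objection to linear normal imputation, which the protocol prespecified. All of this stands. A reader might infer that rounding, or the floor in every case, biases PASI-75; the calculations do not support that.

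The sizes are also unstable. They rest on assumptions, and the wider grid passes 4 and 2 points, so neither figure is a ceiling. Nor is 25% a forecast: SAP 7 says "It is assumed that up to 25% of the subjects will be lost to follow-up by 12 weeks". Under SAP 11.4, "Early termination and unscheduled visits will be re-numbered to an analysis visit based on their windowed visits defined by actual study day", so early termination visits from Day 71 can count as Week 12, and the missing share should be below the dropout share.

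The remedy is imperfect too. Matching by arm stayed within 0.5 points in the 27 scenarios but ranged from −1.4 to +1.2 under other shapes. The −1.4 arose with bimodal response, where matching averaged −0.6 against −3.1 (redrawn) and −2.5 (set to 0), so it still did better there.

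On %BSA, counting whole handprints of about 1% yields integers, and fractions are possible but not required. That stands: integer rounding does no measurable harm to %BSA, and only the floor does.

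Finally, the OC, TF, LOCF and PP analyses do not use this model. They could reveal a distortion but would not correct the primary estimate. It may also be said that the integer rule was meant for PGA only. The text does not say so, and its one exception concerns convergence.

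**Conclusion.** The rule is wrong for PASI and %BSA as stated, and it should be changed before unblinding. The mismatch with the scales and the shifting cut-offs follow from the documents and arithmetic alone. The shrinkage of the PASI-75 difference depends on assumptions: at 25% missing, roughly 1 to 4 points if negatives are redrawn (the floor adding materially) and roughly 0 to 2 if they are set to 0 (mostly the normal model). These are illustrations, not bounds. The effect falls with less missing data. The %BSA difference shrinks by a few percent because of the floor, and the direction for PASI-90 depends on how the floor works.

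Stronger readings are tempting but not supported:

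- **The primary result is compromised.** PGA is an integer score, so its cut-off is unaffected.
- **A false positive is likely.** The bias is mainly against tapinarof. With equal 20% response in both arms, shifts were under 0.4 points with both signs.
- **Power collapses.** Taking 2 or 4 points off 35% v 20% in the pooled formula gives 87.3% or 75.2%. That calculation uses complete-data standard errors and takes the whole shift off the tapinarof rate. Simulating the imputed analysis showed losses under 2 points in the settings tried. A reversed conclusion is unlikely.

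**What to change.** Before unblinding:

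- Limit the integer rule to PGA, with range 0-4.
- Impute PASI and %BSA on their own scales with a method that respects the bound at 0 and the skew. One option is predictive mean matching (FCS REGPMM) separately by treatment arm, with the number of donors fixed in advance, baseline PGA kept as a covariate, and the other covariates and seed unchanged. Matched values need neither ROUND nor MINIMUM.
- Give the PROC MI code for all three variables, including the options actually used for PGA.
- List the change in SAP 13, which, apart from SF-36, now says: "No other changes from the protocol in planned analyses are noted".

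At minimum, if regression is kept, round PASI to 0.1. That restores one cut-off for all subjects but leaves the bias from the normal model and any floor (27 scenarios, 25% missing: −0.9 to −4.2 redrawn, −0.2 to −1.9 set to 0).

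The cost is a few lines of text and code, a documented departure from protocol 10.6, and a smaller donor pool in the vehicle arm: 0.75 × 167 ≈ 125 at 25% missing, of whom 10%, or 12-13, fall in each of the PGA 2 and PGA 4 strata. That is why baseline PGA should be a covariate and not a matching stratum. At 333/167 with 5 donors, the simulated mean PASI-75 difference stayed within 0.2 points of full data.

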### 11. DATA CONVENTIONS FOR ANALYSIS

### 11.1 General Statistical Principles

All statistical tests will be performed at the 0.05 (two-sided) level of significance.

All observed and derived variables (e.g., change from baseline, percentage change from baseline, and response status) that are analyzed or summarized will be listed by subject. Descriptive statistics will provide an overview of the efficacy and safety results. For categorical parameters, the number and percentage of subjects in each category will be presented. The denominator for percentage will be appropriate for the purpose of the analysis. For continuous parameters, descriptive statistics will include number of subjects, mean, standard deviation (SD), median, minimum, and maximum.

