### 12.8 Efficacy Analyses

All efficacy outcomes will be analyzed in the ITT population. Only the primary and secondary efficacy endpoints will be analyzed in the PP population as supportive analyses, as summarized in the Table below.

Efficacy Endpoints	Primary	Sensitivity Analysis
Efficacy Enapoints	1 1 1111ttl y	Schister vicy randingsis

	Analysis	
Discoura Parla sint		ITT, OC
Primary Endpoint	ITT, MI	ITT, TF
PGA response at Week 12		ITT, LOCF
		PP, OC
Secondary Endpoints	ITT, MI	ITT, OC
Categorical Endpoint:	111,1,11	ITT, TF (categorical
PASI-75 at Week 12		endpoint)
• PGA 0 or 1 at Week 12		ITT, LOCF
PASI-90 at Week 12     PASI-90 at Week 12		PP, OC
Continuous Endpoint:		
Change in %BSA at Week 12		
-	ITT, OC	N/A
Exploratory Endpoints	111,00	IN/A
Time to PGA response	TTTT 3.67	TTTT 0.0
Exploratory Endpoints	ITT, MI	ITT, OC
• PGA 0 or 1 at Weeks 2, 4, and 8		

 
PGA response at Weeks 2, 4, and 8
 
		
• Change in PASI from Baseline at Weeks 2, 4, 8, and		
12		
• % change in PASI from Baseline at Weeks 2, 4, 8,		
and 12		

 
PASI-50 at Weeks 2, 4, 8, and 12
 
		

 
PASI-75 at Weeks 2, 4, and 8
 
		

 
PASI-90 at Weeks 2, 4, and 8
 
		
• Change in %BSA from Baseline at Weeks 2, 4, and 8		
• % change in %BSA from Baseline at Weeks 2, 4, 8,		
and 12		
Other Endpoints	ITT, OC	N/A

 
Change from Baseline in Peak NRS at Weeks 2, 4,
 
		
6, 8, 10, 12 and 16		

 
% change from Baseline in Peak NRS at Weeks 2, 4,
 
		
6, 8, 10, 12 and 16		

 
Peak NRS 4-point Responder at Weeks 2, 4, 6, 8, 10, 12 and 16
 
		
Change from Baseline in DLQI at Weeks 4, 12, and		
16		

 
% change from Baseline in DLQI Total Score at Weeks 4, 12 and 16
 
		
• Change from Baseline in PSD at Weeks 2, 4, 8, 12, and 16		

 
% change from Baseline in PSD Total Score at Weeks 2, 4, 8, 12 and 16
 
		
• Change from Baseline in SF36 at Weeks 4, 12, and 16		

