### 12.8.3 Other Efficacy Analyses

Change from baseline in DLQI, PSD, SF-36, and Peak Pruritus-NRS will be analyzed using an ANCOVA model with treatment as a main effect, baseline PGA score as a categorical covariate, and baseline value of the endpoint as a covariate. Percent change from baseline in DLQI, PSD and Peak Pruritus-NRS will be summarized and analyzed using the same method.

In addition, the proportion of subjects with at least a 4-point reduction from baseline in the Peak Pruritus-NRS among subjects with a baseline NRS score  $\geq$  4 will be summarized and analyzed following the same method as the dichotomized secondary endpoints. A plot will be used to illustrate this information.

Subject itch diary and in-clinic itch score assessments will be listed and summarized using descriptive statistics by day. If a subject completed diary itch score on the date of in-clinic visit, the itch score assessed in-clinic will be used in the summary. Change from baseline, treatment difference (Tapinarof cream 1% – Vehicle Cream) in mean change from baseline values and its associated 95% CI will be summarized by day. In addition, the treatment difference and its associated 95% CI will be plotted by day.

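### Subject-reported outcomes are analysed on observed cases only, an undeclared departure from the protocol's imputation rule, and the SAP gives conflicting missing-data rules for the 4-point itch responder

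*SAP*

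**What the plan says.** - **Missing data.** SAP 9 creates imputed datasets for PGA, PASI and %BSA only, bars imputation after Week 12, and adds: "Missing functional outcomes, quality of life endpoints or safety endpoints will not be imputed".
- **Analysis table.** SAP 12.8 puts change in Peak Pruritus-NRS, DLQI, PSD and SF-36 under ITT with observed cases (OC), and enters not applicable for sensitivity analysis. The same row includes "Peak NRS 4-point Responder at Weeks 2, 4, 6, 8, 10, 12 and 16". Apart from time to PGA response, the exploratory PGA, PASI and %BSA endpoints have multiple imputation (MI) as the main analysis and OC as sensitivity.
- **Model.** SAP 12.8.3 uses ANCOVA with treatment, baseline PGA and baseline score. No visit or repeated-measures term is named.
- **Itch responder.** SAP 12.8.3 says that the proportion with a 4-point reduction "will be summarized and analyzed following the same method as the dichotomized secondary endpoints". SAP 12.8.2 gives those secondary endpoints the primary method, which SAP 12.8.1 defines as stratified CMH on imputed data.
- **Expected loss.** SAP 7: "It is assumed that up to 25% of the subjects will be lost to follow-up by 12 weeks".
- **Protocol.** Section 10.6 makes MI the primary way to handle missing data and states no exception. Sections 3.1 and 6.2 count the subject-reported scales among the efficacy assessments. SAP 13 declares the SF-36 scoring change and the COVID-19 additions, and says that nothing else changed.

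**The concern.** A subject with itch scores through Week 8 or Week 10 who is missing at Week 12 contributes nothing to the Week 12 comparison, although those scores predict the missing one. The PASI of the same subject would be imputed from earlier visits. If loss differs between arms and is related to symptoms, OC compares selected completers, and no planned analysis would reveal it. The effect on symptoms and daily life is a stated secondary objective, and p-values will be produced, since SAP 11.1 says "All statistical tests will be performed at the 0.05 (two-sided) level of significance".

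The responder conflict is separate and needs no assumption about dropout: two programmers following different sentences of the same SAP would run different analyses. The third issue is traceability, because a reader of SAP 13 would not learn that these endpoints left the protocol's missing-data rule.

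**Working it through.** **1. The plan's own figure.** SAP 7: "With 500 subjects randomized in a 2:1 ratio" (about 333 and 167) and "40% for subjects receiving tapinarof compared with 15% for subjects receiving vehicle control" for PGA response. Fisher exact power at two-sided 0.05 is above 99.9% (stated: above 99%). For 35% versus 20% it is 93.8% by Fisher enumeration and 94.5% by the pooled normal approximation (stated: above 94%). The figures reproduce to within rounding or method. They concern the primary endpoint only; the documents give no SD or power for the subject-reported scales.

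**2. Precision at the assumed loss.** With 25% missing in each arm, 333 and 167 become about 250 and 125. The standard error of a mean difference rises by √[(1/250 + 1/125) / (1/333 + 1/167)] = √(0.01200/0.00899) = 1.155.

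**3. Bias, illustration A (itch scale).** Assumed: mean NRS falling from 5.8 to 2.5 versus 4.2, SD 2.3 to 2.6, visit correlations 0.6 to 0.85, about 25% overall loss; 2,500 simulated trials per scenario.
- Dropout unrelated to scores: no bias. Empirical standard error is 0.223 for OC and 0.214 using earlier visits; (0.223/0.214)² = 1.086, so about 9% more effective sample size.
- Dropout depending on the last observed score, with loss of 23% versus 30% or 22% versus 33%: the true difference of −1.70 becomes −1.64 or −1.58 under OC. Attenuation is 0.06/1.70 = 3.5% or 0.12/1.70 = 7.1%. The model using earlier visits returns −1.70.
- OC raises the 4-point responder rate by about 2 to 3 points in both arms; the difference hardly moves.

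**4. Bias, illustration B (standardized scale).** Assumed: true Week 12 effect 0.50 SD, four post-baseline visits, correlation 0.5 or 0.7, 1,500 trials per setting. Each cell gives the estimate for correlation 0.5 / 0.7.

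| Loss, tapinarof / vehicle | Dropout depends on | OC | Earlier visits used |
|---|---|---|---|
| 25% / 25% | nothing | 0.498 / 0.500 | 0.498 / 0.499 |
| 25% / 25% | poor response, both arms | 0.500 / 0.499 | 0.500 / 0.499 |
| 20% / 35% | poor response, both arms | 0.463 / 0.464 | 0.503 / 0.499 |
| 15% / 45% | poor response, both arms | 0.420 / 0.434 | 0.497 / 0.503 |
| 25% / 25% | good response on tapinarof, poor on vehicle | 0.374 / 0.392 | 0.500 / 0.501 |

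Against 0.50, OC loses nothing in the first two rows, then about 7%, 13 to 16%, and 22 to 25%. The second row is the important check: dropout depends on observed scores, yet OC is unbiased because loss and mechanism match between arms.

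**5. The responder rule, side by side.**

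| Source | Rule it leads to |
|---|---|
| SAP 12.8.3, through 12.8.2 and 12.8.1 | stratified CMH on imputed data |
| SAP 12.8 table | OC, including Week 16 |
| SAP 9 | no imputation; no NRS imputation model; nothing imputed after Week 12 |

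**6. Earlier data available for a missing Week 12 value (Protocol Table 1).** NRS: Weeks 2, 4, 6, 8 and 10. PSD: Weeks 2, 4 and 8. DLQI and SF-36: Week 4 only, so the gain is smaller for these two.

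**The case against.** **Open choice, protocol model.** OC is stated plainly in SAP 9 and the 12.8 table, and Protocol 10.4.4 names ANCOVA for these four instruments. That stands in favour of keeping the ANCOVA. It does not settle the missing-data rule, which Protocol 10.6 sets separately. The wording of 10.6 is so broad that its intended reach is partly inferred, but the protocol itself lists these scales as efficacy assessments.

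**The conflict is only wording.** The same method could mean just the CMH test, since SAP 12.8.1 also applies CMH to OC data. The missing NRS imputation model and the Week 16 entry favour OC. This is a fair reading, but the SAP does not state it, and illustration A suggests that the responder difference may change little either way.

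**The 25% is not the missing rate for these scales.** This stands. Protocol 7.5 collects all four instruments at early termination, and SAP 11.4 says "Early termination and unscheduled visits will be re-numbered to an analysis visit based on their windowed visits defined by actual study day", so the Week 12 rate could be lower. For the PSD total it could be higher, because one blank item voids it.

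**Stronger readings that a reader might infer.**
- *OC is biased whenever dropout depends on scores.* The second row of illustration B shows otherwise, and nothing in the documents establishes that loss will differ between arms.
- *DLQI and SF-36 need their own visit windows because early-termination scores falling in Week 2 or Week 8 are not analysed.* The mapping is as described, but its cost cannot be counted. SAP 7's figure is for subjects lost to follow-up, whom Protocol 4.7 defines as not returning and not reachable, so they would generally not attend a termination visit. Wider windows would also label scores from the first days of treatment as Week 4, although many SF-36 items look back four weeks.

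**Conclusion.** The point holds as a recommended change. Three things follow from the text, the first by natural reading as regards one visit at a time: the continuous subject-reported scores are analysed on OC visit by visit without a sensitivity analysis; this departs from Protocol 10.6 and SAP 13 does not say so; and the SAP points in two directions on the 4-point itch responder.

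The size of any bias is illustrative. It was nil when amount and mechanism of loss matched between arms, 4 to 7% toward the null under modest differences, and up to about 25% under strong ones. Means, SDs, correlations and dropout models are all assumptions. Using earlier visits removed the bias in these missing-at-random settings, but would not do so if dropout depended on unobserved scores. Precision improves only slightly.

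A reader might also infer that the main efficacy claim is at risk. It is not: these endpoints are exploratory and outside the fixed sequence in SAP 11.6, so the primary and secondary conclusions are unaffected.

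**What to change.** Before database lock and unblinding:

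1. **SAP 9, 12.8 and 12.8.3, continuous scores.** Through Week 12, use earlier visits. The preferred route is FCS imputation feeding the protocol-named ANCOVA, with percent change derived from the same imputed scores. Bound imputed values to each scale: 0 to 10 for NRS, 0 to 30 for the DLQI total, 0 to 160 (16 × 10) for the PSD total. The ROUND and MINIMUM options in SAP 9 set no upper limit. An MMRM is an acceptable alternative. Keep OC ANCOVA as sensitivity, and OC at Week 16.
2. **Itch responder.** Derive it from the same NRS imputations, among subjects with baseline NRS of at least 4, with stratified CMH through Week 12. Keep OC at Week 16, consistent with SAP 9. State this identically in all three sections.
3. **SAP 13.** If OC stays primary for any of these endpoints, list it as a change from Protocol 10.6.
4. **SAP 11.4.** Leave the visit windows as they are.

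Cost: SAP wording and modest programming. Imputing every analysed score separately would need 1 (NRS) + 7 (DLQI) + 17 (PSD) + 8 (SF-36) = 33 models; an MMRM avoids imputation for the continuous scores. The results become model-based under missing at random, as the imputed PASI and %BSA results already are.
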